6.3 Administration of Decitabine

Lev	Decitabine	G-CSF	Cladribine	Cytarabine	Mitoxantrone
el	(20 mg/m ² IV) ^{1,2}	(SQ, D0 to D5) ³	$(IV, D1 \text{ to } D5)^1$	(IV, D1 to D5) ^{1,4}	$(IV, D1 \text{ to } D3)^{1}$
1	10 days (D1 to D10)	300 or 480 μg	5 mg/m ²	2 g/m ²	18 mg/m ²
-1	7 days (D1 to D7)	300 or 480 μg	5 mg/m ²	2 g/m ²	ND: 18 mg/m ²
-2	5 days (D1 to D5)	300 or 480 μg	5 mg/m ²	2 g/m ²	ND: 18 mg/m ²

Dose Escalation Scheme for Reference

¹Dosing based on actual patient weight. ²Administered immediately prior to other chemotherapy. ³Dosing based on patient weight: <76 kg vs. \geq 76 kg; D0 and D1 dose may be omitted if WBC >20,000/µL. ⁴Started 2h after completion of cladribine.

- **6.3.1** Patients will receive decitabine at a pre-specified dose level described below. If dose Level 1 is found to be too toxic, therapy will be de-escalated to Level -1. If dose Level -1 is found to be too toxic, therapy will be de-escalated to level -2.
 - *Level 1*: 10 days of decitabine (day 1 to day 10). The total dose of decitabine delivered will be 200 mg/m² for Level 1.
 - Level -1: 7 days of decitabine (day 1 to day 7). The total dose of decitabine delivered will be 140 mg/m² for Level -1.
 - *Level -2*: 5 days of decitabine (day 1 to day 5). The total dose of decitabine delivered will be 100 mg/m² for Level -2.
- 6.3.2 The dose of decitabine is calculated using the patient's actual weight.
- **6.3.3** Decitabine will be administered IV as per institutional standards.
- 6.3.4 Administration in the outpatient clinic is permitted.

- 6.3.5 All treatment is given as intent-to-treat; missed doses will not be made up.
- **6.3.6** No investigational or commercial agents or therapies other than those described herein may be administered with the intent to treat the patient's malignancy.

6.4 Administration of G-CSF, Cladribine, Cytarabine, and Mitoxantrone

- 6.4.1 The dose of the G-CLAM chemotherapy will be as follows: G-CSF 300 or 480 μg (based on actual weight: <76 kg vs. ≥76 kg) subcutaneously daily on Days 0-5, cladribine 5 mg/m² daily IV over 2 hours on Days 1-5, cytarabine 2 g/m² daily IV over 2 hours on Days 1-5, and mitoxantrone 18 mg/m² daily IV over 60 minutes on days 1-3. Note that we refer to the first day of G-CLAM induction as Day +1.
- 6.4.2 The doses of G-CLAM are calculated using the patient's actual weight.
- 6.4.3 If WBC >20,000/ μ L, Day 0 and Day 1 G-CSF may be omitted at provider discretion.
- **6.4.4** Administration in the outpatient clinic can be considered but should be discussed with the study investigators.
- 6.4.5 All treatment is given as intent-to-treat; missed doses will not be made up.
- **6.4.6** No investigational or commercial agents or therapies other than those described herein may be administered with the intent to treat the patient's malignancy.

6.5 Monitoring during/after Induction Therapy

For patient monitoring, the following studies and study intervals are suggested:

- **6.5.1** Complete blood counts with differential blood count, including immature cells/blasts, and platelet count at least 3 times weekly until ANC >1,000/ μ L and then at least weekly until platelet count >100,000/ μ L.
- **6.5.2** Metabolic panel, including electrolytes (Na, K), bilirubin, ALT/AST, and creatinine at least weekly until ANC >1,000/ μ L and platelet count >100,000/ μ L.
- **6.5.3** If patients develop signs or symptoms suggestive of cardiac dysfunction, LVEF should be assessed using the same method to evaluate baseline LVEF status (MUGA scan or echocardiography, or other appropriate diagnostic modality).

6.6 Assessment for Response after First Induction Course

A bone marrow aspirate should be obtained upon blood count recovery (i.e. ANC >1,000/ μ L and platelet count >100,000/ μ L) or between Days +25 to +35 after start of G-CLAM chemotherapy, whichever occurs first; a bone marrow biopsy should be obtained if spicules are absent from the aspirate sample. In patients with unclear response status, the bone marrow examination should be repeated every 7-10 days until the response can be assessed or until Day +45.

- **6.6.1** Patients achieving MRDneg CR: Patients are eligible for consolidation chemotherapy, as described in section 6.8.
- **6.6.2** Patients achieving CR with MRD, CRi, or those with persistent disease: patients are eligible for a second course of induction chemotherapy consisting of G-CLAM without decitabine provided all non-hematologic toxicities have resolved

to Grade <2. For patients who experienced \geq Grade 3 non-hematologic / noninfectious toxicity during the first induction, a dose reduction is recommended as described in section 6.7. Patients who achieve CR or CRi after a second induction are eligible to receive consolidation chemotherapy, as described in section 6.8.

6.6.3 Patients with persistent aplasia without evidence of disease after Day +45: patients will be removed from protocol.

6.7 Dose Modifications of Chemotherapeutic Drugs for Initial and Subsequent Treatment Cycles

The following dose modifications are suggested both for induction cycle #1 (i.e. if organ function parameters worsen between baseline and start of chemotherapy) and subsequent treatment cycles:

- 6.7.1 If a patient develops Grade ≥ 3 non-hematologic toxicity other than Grade 3 infections within 21 days from the last dose of G-CLAM, subsequent doses of cladribine and cytarabine will be reduced by 25% and the dose of mitoxantrone will drop by 2 mg/m². The patient may receive future cycles using this dosereduced regimen, if the patient demonstrated potential response and once the nonhematologic toxicity has resolved to a level of < Grade 2. If a patient develops Grade \geq 3 non-hematologic toxicity other than Grade 3 infection within 21 days from the last dose of the first dose-reduced regimen, the dose of the cladribine and cytarabine for subsequent cycles will be reduced by 50%. Mitoxantrone will only be given for 1st and 2nd induction and is not part of post-remission chemotherapy. and so further dose reductions will not be required. The patient may receive future cycles using the new dose-reduced regimen, if the patient demonstrated potential response and once the non-hematologic toxicity has resolved to a level of < Grade 2, unless, at any time, a patient displays Grade ≥ 3 non-hematologic toxicity other than Grade 3 infections while receiving the 50% dose-reduced regimen, at which point the patient will not be eligible for additional therapy as part of the protocol. Furthermore, if patients require treatment interruption of > 21days from the planned start of the next cycle, the patient will be not be eligible for additional therapy as part of the protocol.
- 6.7.2 Mitoxantrone: Consider dose reduction of mitoxantrone by 50% if the bilirubin concentration is $1.5-4.5 \times IULN$. The dose of mitoxantrone will be reduced to 25% if the bilirubin concentration is >4.5 x IULN.
- 6.7.3 Cladribine: If the serum creatinine exceeds 2.0 mg/dL and/or estimated creatinine clearance (calculated by Cockcroft-Gault) decreases to less than 50 mL/min during therapy, we will consider dose reduction in discussion with the Oncology Pharmacist.
- **6.7.4** Cytarabine: If the serum creatinine exceeds 2.0 mg/dL and/or estimated creatinine clearance (calculated by Cockcroft-Gault) decreases to less than 50 mL/min during therapy, we will consider dose reduction in discussion with the Oncology Pharmacist.

6.8 Consolidation Therapy

After a achieving MRDneg CR after 1 cycle of decitabine + G-CLAM or after achieving CR/CRi after 1 cycle of decitabine + G-CLAM followed by GCLAM without decitabine, patients are eligible for consolidation therapy with G-CLA. Consolidation will not include decitabine.

- **6.8.1** The treatment is identical to the induction course but without decitabine or mitoxantrone (i.e. G-CSF, cladribine, and cytarabine, "G-CLA"), provided the patient had <Grade 3-4 non-hematologic / non-infectious toxicity during induction. If there was such toxicity, doses should be reduced as described in section 6.7.
- **6.82** Consolidation courses should start within 6 weeks of response assessment once patients have recovered to Grade ≤ 2 toxicities from the previous course of therapy.
- **6.8.3** Patients can receive up to 4 courses of consolidation therapy.
- **6.8.4** Patients can proceed to transplantation barring contraindications and if a suitable donor is available.

6.9 Supportive Therapy

- **6.9.1** All patients will be adequately hydrated and receive appropriate anti-emetics based upon NCCN guidelines [24].
- **6.9.1** Growth factors may be used according to institutional practice guidelines or the preference of the attending physician.
- **6.9.2** Antimicrobial prophylaxis should be used according to institutional practice guidelines. In case of neutropenic fever, standard diagnostic testing will be performed, and empiric antibiotic coverage will be utilized as per usual care and standard institutional practices (SCCA, UWMC, and Fred Hutch).
- **6.9.3** Transfusional support should be carried out according to institutional practice guidelines.

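### For a Grade 4 infection within 21 days of the last induction G-CLAM dose, section 6.7.1 reduces later doses, section 6.8.1 keeps consolidation unreduced, and section 6.6.2 implies no reduction

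*Combined protocol and SAP*

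**What the plan says.** Three sections of the combined protocol and SAP decide whether doses fall after a toxic induction course.

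- **Section 6.7.1 (dose modifications).** The trigger is Grade 3 or higher "non-hematologic toxicity other than Grade 3 infections within 21 days from the last dose of G-CLAM". Once it is met, "subsequent doses of cladribine and cytarabine will be reduced by 25" percent, and mitoxantrone drops by 2 mg/m². The same exemption, limited to Grade 3 infection, recurs for the further cut to 50%, "non-hematologic toxicity other than Grade 3 infection within 21 days from the last dose of the first dose-reduced regimen", and for the end of protocol therapy, "non-hematologic toxicity other than Grade 3 infections while receiving the 50% dose-reduced regimen". The lead-in to section 6.7 presents all of this as suggested.
- **Section 6.6.2 (before a second induction).** For patients with at least "Grade 3 non-hematologic / noninfectious toxicity during the first induction, a dose reduction is recommended as described in section 6.7".
- **Section 6.8.1 (consolidation).** Treatment is the induction regimen without decitabine and mitoxantrone, otherwise unchanged, provided the patient had less than Grade 3-4 "non-hematologic / non-infectious toxicity during induction". If there was such toxicity, doses should come down as set out in section 6.7.

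Sections 6.6.2 and 6.8.1 both refer to section 6.7, whose own trigger differs from theirs. No order of precedence is given.

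**The concern.** The exemption in 6.7.1 covers Grade 3 infection only. The one in 6.6.2 and 6.8.1 covers infection of any grade. A patient whose only severe non-hematologic event is a Grade 4 infection therefore gets a different answer depending on which section the treating team reads.

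Neither wording looks like a slip: the narrow exemption appears three times in 6.7.1, and the broad one appears in two separate sections. The event is also foreseeable. The background reports that 5 of 9 deaths among 52 patients given decitabine-primed MEC were related to infection. Its account of G-CLAM alone sets infections and neutropenic fever apart before naming the other common Grade 3+ events.

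At stake is uniform treatment after a severe event. For patients who go on to a second induction, the dose is also part of the regimen being judged, because section 8.5 takes the best response over at most two induction courses.

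**Working it through.** No sample size, power or error rate enters here. The check compares the three triggers on defined cases and then sizes the difference in dose.

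**Step 1. The triggers on test cases.** Each case is the patient's only Grade 3 or higher non-hematologic event, occurring in the first induction. The window is the 21 days after the last G-CLAM dose in 6.7.1.

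| Case | 6.7.1 | 6.6.2 (second induction) | 6.8.1 (consolidation) | Agree? |
|---|---|---|---|---|
| Grade 3 infection, in window | exempt, no reduction | trigger not met | unreduced | yes |
| Grade 4 infection, in window | reduce | trigger not met | unreduced | **no** |
| Grade 4 infection, after window | trigger not met | trigger not met | unreduced | yes |
| Grade 3-4 noninfectious, in window | reduce | reduce | reduce | yes |

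On infection, the disagreement is confined to Grade 4 events inside the window.

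**Step 2. Direct or implied.** Section 6.8.1 states positively that treatment is unchanged when its condition holds, so it contradicts 6.7.1. Section 6.6.2 names the patients for whom a reduction is recommended and is silent on the rest, so it differs from 6.7.1 only by implication.

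**Step 3. The time window.** Section 6.4.1 ends G-CLAM on Day 5, so the 6.7.1 window closes on Day 5 + 21 = Day 26. Sections 6.6.2 and 6.8.1 speak of toxicity during induction without a day count, and section 6.6 allows response assessment to run to Day +45. The time limits therefore differ as well as the exemptions.

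**Step 4. Size of the difference.** Full doses are from sections 6.3 and 6.4.1, and the reductions are from 6.7.1.

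- Cladribine: 5 × (1 − 0.25) = 3.75 mg/m², against 5 mg/m².
- Cytarabine: 2 × (1 − 0.25) = 1.5 g/m², against 2 g/m².
- Mitoxantrone: 18 − 2 = 16 mg/m², against 18 mg/m².

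The first two apply to a second induction or to consolidation. The mitoxantrone difference applies to a second induction only, since consolidation contains none.

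**Step 5. Reach into the primary endpoint.** Consolidation comes after the inductions whose best response is counted, so its dose cannot alter that response. Only the second-induction dose can. The patients concerned had a Grade 4 infection in the window, had not reached CR without measurable residual disease, recovered enough to continue, and received a second induction. The documents give no rate for this combination, so no count follows.

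**The case against.** The strongest reply is that section 6.7 is guidance. Its lead-in calls the modifications suggested, 6.6.2 recommends, and 6.8.1 says should; only the sentence inside 6.7.1 says will. On this view 6.6.2 and 6.8.1 are shorthand pointers to the section that carries the detail. That is a plausible reading, and it rules out saying that the protocol strictly requires a reduction and also forbids it. It does not remove the conflict: guidance with two answers for one event is still inconsistent, 6.8.1 affirmatively keeps doses unchanged, and nothing gives 6.7 precedence.

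A reader might infer more than the documents support on four counts.

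- *That infection has no consequence under 6.6.2 and 6.8.* It does. Section 6.6.2 makes a second induction wait until non-hematologic toxicity is below Grade 2, with no infection exemption, and section 6.8 makes consolidation wait for recovery to Grade 2 or less. What is missing there is a dose-reduction trigger.
- *That the stopping rule at the 50% level is part of the conflict.* It is not. The 50% regimen follows toxicity on an already reduced course, so it is the third course at the earliest, which is consolidation. Sections 6.6.2 and 6.8.1 address toxicity during induction only.
- *That every Grade 4 infection in Cycle 1 is affected.* Later infections fall outside the 6.7.1 window, and there the sections agree.
- *That the dose-limiting toxicity definition settles the matter.* Section 8.3.2 treats Grade 4 infection in yet another way, but for trial monitoring rather than dosing of the next course.

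**Conclusion.** The inconsistency is real and narrow. For a Grade 4 infection within 21 days of the last G-CLAM dose of induction, 6.7.1 and 6.8.1 give opposite answers on consolidation dose, and 6.6.2 departs from 6.7.1 by implication on second-induction dose. Per patient, the size is 25% of the cladribine and cytarabine dose, plus 2 mg/m² of mitoxantrone where a second induction is given.

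It might be tempting to conclude that the primary result is compromised. The documents do not support that. The two-stage cut-offs (13 of 19, 31 of 41) and the stated error rates are unaffected, only the second-induction branch touches the endpoint, and the number of patients in it is unknown.

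The endpoint link assumes that sections 6.6.2 and 8.5, which provide for a second induction, are the operative text. The background update says that patients without the target response leave the study. If that governed, only the consolidation conflict would remain, and the primary endpoint would not be touched. This is a minor point, worth correcting because it concerns dosing after a severe event that can be expected to occur.

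**What to change.** The sponsor should reconcile sections 6.6.2, 6.7.1 and 6.8.1 on three items:

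1. the infection exemption, so that one rule covers Grade 4 infection;
2. the time window, so that all three sections count toxicity over the same period;
3. the force of the wording, which now ranges over suggested, recommended, should and will.

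Which rule to adopt is for the investigators to decide; this review does not propose one. The simplest drafting is to state the trigger once and have the other two sections refer to it without restating it.

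The cost is protocol wording only. No sample size, cut-off or analysis changes, and no new data collection is needed: pharmacy dispensing records are already source documents under section 9.0, so the second-induction dose received can be tabulated beside response if wanted.

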6.10 Treatment of CNS Disease

Treatment of CNS disease is done according to institutional practice guidelines or the preference of the attending physician.

6.11 Recommended Follow-up Care

After completion of protocol treatment, patients should be evaluated by treating physicians according to institutional and/or national guidelines or the discretion of the attending physician. These evaluations may include peripheral blood studies and/or bone marrow examinations, as clinically indicated.

6.12 Criteria for Removal from Treatment

All reasons for discontinuation of treatment must be documented:

6.12.1 Completion of protocol treatment.

- 6.12.2 Consolidation with HCT after achievement of CR or CRi.
- 6.12.3 Failure to achieve CR or CRi after at most 2 induction cycles.

6.12.4 Persistent aplasia without evidence of leukemia after Day +45.

6.12.5 Relapse after achievement of CR or CRi during treatment.

6.12.6 Adverse toxicities that prevent continuation with study treatment.

6.12.7 The patient may withdraw from the study at any time for any reason.

6.13 Concomitant Medications

Patients may take concomitant medications other than active anti-AML therapy while receiving study drugs.

7.0 INFORMATION ON STUDY DRUGS

7.1 Drug Information on Decitabine (5-Aza-2'-deoxycytidine)

- 7.1.1 Mechanism of action: The exact mechanism of action for decitabine is unknown. As a cytosine analog, decitabine is converted to a deoxynucleotide triphosphate form and incorporated into DNA during cell division in lieu of cytosine [25]. At lower concentrations (0.001-1 μ M), its incorporation into DNA traps and depletes DNA methyltransferases (MTases), leading to depletion of methylated DNA in cell progeny [14, 25]. At higher concentrations (>1 μ M), incorporation of the drug into DNA probably leads to a large number of DNA breaks, initiating proapoptotic signals and cell death [14].
- 7.1.2 Human pharmacokinetics: The peak decitabine concentration after 20-30 mg/m² infused over 1 hour is reached in approximately 30 minutes after completion of the infusion and approaches 0.5 μ M. Decitabine is rapidly cleared from the plasma in a biphasic manner: an initial rapid phase has a very short half- life (t_{1/2α} = 7 minutes), such that the decitabine concentration falls below 0.01 μ M within 1 hour after completion of the infusion; the half- life of the second clearance phase is more prolonged (t_{1/2β} = 30 minutes) [26]. Plasma protein binding is negligible (<1%) [27].
- 7.1.3 Human toxicology and adverse events (AEs): *Frequent drug-related AEs* (occurring in 26% -50% of patients) observed in patients treated with standard doses of decitabine (20 mg/m²/day times 5 days) include: anemia, neutropenia, thrombocytopenia, constipation, diarrhea, nausea, fatigue, peripheral edema, pyrexia, cough, and dyspnea. Less frequent drug-related AEs (occurring in 10% 25% of patients) include: febrile neutropenia, anorexia, vomiting, dyspepsia, stomatitis, abdominal pain, asthenia, chills, upper respiratory tract infection, pneumonia, hypokalemia, arthralgia, back pain, pain in extremity, headache, dizziness, insomnia, epistaxis, petechiae, rash, and hypotension. *Infrequent drug-related AEs (occurring in 5% -10% of patients)* include: thrombocythemia, cardiac failure, tachycardia, otalgia, dysphagia, gastro-esophageal reflux, oral pain, toothache, tooth abscess, chest pain, generalized edema, mucosal inflammation, generalized pain, cellulites, oral candidiasis, sinusitis, bacteremia, urinary tract infection, elevated liver function tests, weight loss, dehydration,

hyperglycemia, hypomagnesaemia, bone pain, muscle spasm, weakness, musculoskeletal pain, myalgia, anxiety, confusion, depression, pharyngeal pain, pleural effusion, sinus congestion, dry skin, ecchymosis, skin erythema, night sweats, pruritis, other skin lesions, hypertension, and death. *Rarer drug-related AEs (occurring in <5% of patients)* include: splenomegaly, myocardial infarction, cardio-pulmonary arrest, cardiomyopathy, atrial fibrillation, supraventricular tachycardia, cholecystitis, increased bleeding with and without procedures, fungal infections, sepsis, periventricular abscess, mycobacterium avium infection, mental status changes, renal failure, pulmonary embolism, pulmonary mass, and hypersensitivity reaction [28].

- 7.1.4 Formulation and reconstitution: Decitabine is supplied as a sterile, lyophilized white powder, in single vial. Each vial contains 50 mg of the drug. DAC should be aseptically reconstituted with 10 ml sterile water, providing a concentration of 5.0 mg/ml with a pH 6.7-7.3. Immediately after reconstitution, the reconstituted decitabine solution should be further diluted with 0.9% sodium chloride, 5% dextrose, or lactated Ringers to a final drug concentration of 0.1-1.0 mg/ml.
- 7.1.5 Administration and compatibility: The diluted decitabine solution should be inspected for particulate matter and discoloration prior to IV infusion. If there is evidence of particulate matter or discoloration, the solution should not be infused. Patients should be pre-medicated with anti-emetic therapy as per standard practice.
- **7.1.6** Storage and stability: Vials of non-reconstituted decitabine should be stored at room temperature 25°C (77°F). Unless used within 15 minutes, the diluted decitabine solution must be prepared using cold infusion liquids (2-8°C, 36-46°F) and can be stored at 2-8°C for up to 7 hours.
- 7.1.7 Drug-drug interaction: No formal drug-drug interactions have been studied for decitabine. *Ex vivo* studies in human liver microsomes suggest that decitabine is unlikely to inhibit or induce cytochrome P450 enzymes.
- 7.1.8 Warnings and precautions: *Ex vivo* and *in vivo* animal models have found that decitabine is mutagenic and may harm the fetus, but the effect of DAC on the human fetus has not been systematically examined. Thus, it is considered pregnancy category D. Women should be advised not to become pregnant while receiving decitabine, and men should be advised not to father a child while receiving decitabine and at least 3 months after completing the therapy. It is not known whether decitabine or its metabolites are excreted in breast milk; thus, it is not recommended for lactating females who are breast-feeding. A small percentage of patients will have hypersensitivity reactions to decitabine, and these individuals should not receive the drug again.
- **7.1.9** Recommended dose adjustments for organ dysfunction: There is limited or no data examining the toxicity of decitabine in patients with renal or liver dysfunction. Therefore, administration of decitabine to patients with liver or kidney disease must be done with caution.

